7.2 General considerations for statistical analysis

Data are summarized by treatment group. Continuous variables are summarized using mean and standard deviations. Categorical variables are summarized using frequency and percentages. SAS Enterprise Guide 7.1 is used for analyses.

Demographic and other baseline characteristics are compared between groups. Race, ethnicity, age, gender, language, marital status, baseline primary care provider (PCP) utilization per member per month (PMPM), baseline inpatient utilization PMPM, baseline ED utilization PMPM, and baseline observation visits PMPM are summarized for the Utilization Outcome Cohort. For the Clinical Outcome Cohort, the same characteristics will be summarized, as well as NPI-Q Distress (caregiver distress), NPI-Q Severity (patient symptom severity), PHQ-8 (caregiver depression), and Quick Dementia Rating Scale (patient dementia severity) from the baseline survey.

A combination of t-tests (at $p < .05$), chi square tests (at $p < .05$) and standardized mean differences (cutoff of .15 or greater) were used to identify differences between cohorts and covariates for risk adjusted models. Based on these criteria, race, ethnicity, and age were identified as different between intervention and control in the Utilization Outcome Cohort, as were baseline PCP visits, inpatient hospitalizations, and Observation visits. For the Clinical Outcome Cohort, PHQ-8 (caregiver depression) was different across Intervention and Control. Risk adjusted models for clinical outcomes also adjusted for the demographic characteristics (race, ethnicity, and age) identified for the risk adjusted utilization models in order to maintain consistency across models.

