### **9.4 Data Analyses**

Depending on the type of outcome, we will conduct either a linear, negative binomial, or logistic regression, with random effects for nurses, to account for multiple patients nested within the same nurse. The primary predictor will be intervention (iCMP nurse care manager assignment to early CareEco training versus delayed training). Models will be adjusted for a limited number of baseline covariates: dementia stage and severity; Elixhauser score; and patient characteristics. If there are many unbalanced patient or

nurse characteristics, we will use propensity score weighting to adjust for confounding in the face of the limited sample size. Secondary models will examine process measures as potential mediators of the intervention effect on reported outcomes, clinical outcomes, and utilization outcomes. Subgroup analyses will be explored, but given the limited sample size, we do not expect sufficient power to detect effect modification nor significant intervention effects within subgroups.

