7 GENERAL ANALYSIS CONSIDERATIONS

7.1 Analysis populations

7.1.1 Utilization Outcome Cohort

For ED visit outcome measurement, the validated cohort was then further restricted to those with at least 1 member month of Medicare FFS eligibility and alignment to our ACO in the pre and the post period (Intervention n=126, Control n=105), to allow for sufficient utilization data for measurement. (See Figure 1 of cohort flowchart)

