7.1.2 Clinical Outcome Cohort

For the NPI-Q Distress outcome measurement, the validated cohort was restricted to baseline and follow-up survey respondents with completed NPI-Q Distress measures (Intervention n=35, Control n=28). (See Figure 1 of cohort flowchart)

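### The SAP picks adjustment covariates from observed arm differences by an undefined rule, and so leaves out Elixhauser and dementia severity, which the protocol named in advance

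*SAP*

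**What the plan says.** Protocol 9.4 fixes the kind of adjustment in advance: "Models will be adjusted for a limited number of baseline covariates: dementia stage and severity; Elixhauser score; and patient characteristics". The measures table in Protocol section 6 lists both QDRS and Elixhauser as control variables. For the case of many unbalanced characteristics, Protocol 9.4 foresees propensity score weighting.

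SAP 7.2 works differently. It compares the arms at baseline using t-tests and chi-square tests at p < .05 together with standardized mean differences (SMDs): "standardized mean differences (cutoff of .15 or greater) were used to identify differences between cohorts and covariates for risk adjusted models". It calls this a combination and does not say whether one criterion is enough or several are needed.

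The utilization cohort ("Intervention n=126, Control n=105") has ten candidates: six demographic variables and four baseline utilization rates. Six are reported as different: race, ethnicity, age, PCP visits, inpatient stays and observation visits. The clinical cohort ("Intervention n=35, Control n=28") has the same ten plus four survey scores, the last being "and Quick Dementia Rating Scale (patient dementia severity) from the baseline survey". There the result is: "For the Clinical Outcome Cohort, PHQ-8 (caregiver depression) was different across Intervention and Control". Race, ethnicity and age are then carried into the clinical models for consistency.

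SAP 8.1 adjusts the ED model for the baseline utilization and demographic variables that differed. SAP 8.2 adjusts the NPI-Q model for race, ethnicity, age and baseline PHQ-8.

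**The concern.** Nurses were randomised, so an observed baseline difference is a weak reason to adjust for a variable. The stronger reason is that the variable predicts the outcome, and the protocol's named set reflects that. Under the SAP's rule the model depends on the data, and a cutoff of 0.15 is small against sampling error at these sizes.

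The timing adds to this. SAP 7.1.1 requires at least one eligible member month after training, and SAP 7.1.2 requires a completed follow-up NPI-Q. Baseline comparisons in these cohorts could therefore be run only once follow-up data existed.

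Protocol 9.2 says the pilot is to supply effect sizes for a full-scale study. Adjusted estimates used for that purpose should come from a covariate set that did not depend on the observed arms, and by a rule that a reader can repeat.

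**Working it through.** The documents state no false-flag rate, so there is no figure of theirs to reproduce.

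**Inputs.** Cohort sizes are from SAP 7.1.1 and 7.1.2, and the cutoffs, candidates and flags from SAP 7.2. There are 30 randomised nurses (SAP 5). The within-nurse ICC of baseline covariates is not given; I assume 0 to 0.10. Tests are taken as two-sided.

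**Chance of flagging a covariate with no true difference, if SMD ≥ 0.15 suffices.** SE = √(1/n₁ + 1/n₂) and P = 2·[1 − Φ(0.15 / (SE·√DE))], where DE = 1 + (m − 1)·ICC and m = N/30.

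- Utilization: SE = √(1/126 + 1/105) = 0.132. At ICC 0, 0.15/0.132 = 1.135 and P = 0.256. With m = 231/30 = 7.7, an ICC of 0.05 gives DE = 1 + 6.7 × 0.05 = 1.335 and P = 0.326. An ICC of 0.10 gives DE = 1.67 and P = 0.380.
- Clinical: SE = √(1/35 + 1/28) = 0.254. At ICC 0, 0.15/0.254 = 0.59 and P = 0.554. With m = 63/30 = 2.1, an ICC of 0.10 gives DE = 1.11 and P = 0.574.

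Simulation with 15 clusters per arm gave 25% to 38% and 55% to 58%, in agreement.

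**Relation of the two criteria.** An SMD of 0.15 corresponds to p = 0.26 in the utilization cohort and p = 0.56 in the clinical cohort. Reaching p < .05 needs an SMD of about 0.26 and 0.51 respectively. So the SMD cutoff governs if either criterion suffices, and the test governs if both are needed.

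**Each reading against the reported flags (binomial, covariates treated as independent).**

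| Reading | Utilization: 6 of 10 | Clinical: 1 of 14 |
|---|---|---|
| SMD ≥ 0.15 suffices | expected 2.6 to 3.8; P(≥6) = 0.02 (ICC 0) to 0.13 (ICC 0.10) | expected 7.8 to 8.0; P(≤1) about 0.0002 |
| p < .05 required | expected 0.5; P(≥6) about 3 × 10⁻⁶, or about 6 × 10⁻⁴ if clustering raises test size to 13% | expected 0.7; P(≤1) = 0.85 |

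The SMD reading is tolerable for the first cohort and very poor for the second; the test reading is the reverse.

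**Covariates side by side.**

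| Protocol 9.4 | ED model (SAP 8.1) | NPI-Q model (SAP 8.2) |
|---|---|---|
| Dementia severity (QDRS) | absent | absent, though summarised at baseline |
| Elixhauser | absent | absent |
| Patient characteristics | race, ethnicity, age | race, ethnicity, age |
| not named | flagged baseline utilization | PHQ-8 |

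**The case against.** Much of the case on the other side stands.

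- **Chance as the main explanation.** A reader might infer that the rule mostly flags noise. In the utilization cohort the documents do not support that: chance accounts for about 2.6 to 3.8 of six flags. The groups are also no longer the full randomised arms. SAP 6 reports 206 reduced to 143 (69%) and 187 to 113 (60%), a difference with p = 0.06 ignoring clustering, so some imbalance may come from exclusions after randomisation.
- **A rule that contradicts its own output.** A reader might also infer this from the single clinical flag. It does not follow, because the combination is undefined and requiring p < .05 fits that flag well. The 0.0002 treats 14 variables as independent, although the survey scores are plausibly correlated. If only the four added scores were judged, at most one flag at the 0.15 cutoff has probability 0.446⁴ + 4 × 0.554 × 0.446³ = 0.24. What remains is an undefined rule, possibly applied differently in the two cohorts.
- **An open protocol set.** Patient characteristics is a loose term, and age, race and ethnicity fall within it. The protocol did foresee action on imbalance, but by propensity weighting rather than covariate selection.
- **QDRS is survey-only.** With 50% to 60% of caregivers expected to respond, it cannot cover the ED cohort. That does not explain leaving it out of the NPI-Q model, or leaving out Elixhauser altogether.
- **Limited effect on NPI-Q.** With complete pairs, time-constant covariates entered as main effects leave a linear difference-in-differences estimate unchanged.
- **A feasibility pilot already reported.** The SAP is largely in the past tense, so rewording cannot restore prespecification. The protocol set is still the one that was named in advance.

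**Conclusion.** The point holds in this form: the SAP replaces the protocol's named set, without explanation, with covariates chosen from observed arm differences by a rule whose combination is undefined. Elixhauser is lost from both models, and QDRS from the NPI-Q model where it could have been used.

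If the SMD cutoff alone suffices, a balanced covariate is flagged about 26% of the time at 126/105 (33% at ICC 0.05) and 55% at 35/28. No single reading fits both 6 of 10 and 1 of 14 well. This rests on independent covariates, an assumed ICC range and no true differences; correlation or real imbalance would soften it.

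The practical consequence is mainly for the adjusted ED model. For NPI-Q it depends on how covariates enter, which the SAP does not specify. A reader might go further and conclude that the confidence intervals are invalid or that covariates were chosen to favour a result. The documents give no means of sizing the first and no evidence of the second.

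**What to change.** - Replace the selection rule in SAP 7.2 with the Protocol 9.4 set as the main adjusted analysis, whatever the observed imbalance. Put Elixhauser and a fixed list of patient characteristics (for example age, race and ethnicity) in both models, and QDRS in the NPI-Q model only.
- Do not add baseline ED rate or baseline NPI-Q Distress as covariates in the difference-in-differences models, where they are already the pre-period outcomes. If they are wanted as covariates, model the post-period outcome instead (ANCOVA). Say which is used, for NPI-Q in particular, since time-constant main effects would not move its linear difference-in-differences estimate.
- Keep the SMD table as description. Report the present data-selected model as a sensitivity analysis labelled post hoc, and state how its criteria were combined in each cohort.

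The cost is SAP wording, a model re-run and an acknowledgement that the current model departed from the protocol. The protocol planned to collect both omitted variables; the SAP does not confirm that Elixhauser was derived. If a dropped covariate correlates with the outcome at r, a simple linear model that uses it reduces residual variance by r²: 4% at an assumed r of 0.2, 25% at 0.5. The documents give no r.

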7.3 Missing data

Missing data were not imputed for analyses.

8 STATISTICAL ANALYSES

8.1 Primary outcome analysis

The change in ED visits PMPM from 12 months prior to training to 6 months post-training for intervention and control cohorts are compared using a differences-in-differences model with a negative binomial distribution (to account for utilization count data) and log link. This model estimates a difference-in-differences rate ratio that provides an estimate of the relative rate reduction/increase in ED visits PMPM in the intervention group as compared to controls.

Models included a weight for the number of member months in the pre and post periods, allowing PWD with more member months (and therefore more stable estimates) to contribute more strongly to the intervention effect. The training (“enrollment”) month was not included in either pre or post period. Models adjusted for baseline utilization and demographic characteristics (race, ethnicity, age) that differed across intervention and control cohorts. A sensitivity analysis removed PWD who died in the post period.

We hypothesized high feasibility in measuring ED visits for this population but had no specific hypothesis regarding whether the program would impact ED utilization in the relatively short 6 month-post period.

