### **9.3 Outcomes**

The primary outcome for the is pilot is emergency room visits within 6 months. We will rely on Epic and Medicare claims data for all measures of healthcare service utilization and costs, care intensity / quality, documentation of advance care planning, and documentation of medication review. These outcomes will be assessed for all PWD who are cared for by selected nurse care managers using retrospective analysis of existing health care data. We anticipate that this will include 150 PWD among care managers who receive early training and 150 PWD who receive delayed training. These data are housed in an existing data repository; we anticipate minimal missing data. Key secondary outcomes will assess the number of contacts between nurse care managers and care partners, and documented advance care planning; these measures likewise available from the existing data warehouse and we anticipate minimal missing data.

In order to ensure systematic capture of key clinical outcomes within this pilot, we will survey caregivers of PWD receiving care management from the 30 selected nurse care managers and meeting our inclusion and exclusion criteria at months 3 and 9. We expect that a minimum of 50% of caregivers will complete each survey, yielding an expected sample of 75 PWD caregiver respondents completing each survey and 37 PWD caregiver respondents completing both an initial and follow- up survey for nurses assigned to the early and the delayed training. We will assess the completeness and correlation of behavioral symptoms of dementia, caregiver depression, caregiver burden, and PWD quality of life captured via trained nurse care managers (and documented in Epic or iCMP data) with caregiver survey responses.

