2.2 Primary outcome measure

The primary outcome is the change in ED visits per member per month from the 12 months prior the adapted Care Ecosystem training to the 6 months post training.

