3 STUDY METHOD

This is a pragmatic randomized quality improvement pilot trial to assess the feasibility and effectiveness of an adapted Care Ecosystem dementia care training for pre-existing nurse care managers who provide care management to high-risk patients. 15 integrated care management program (iCMP) nurse care managers were randomly assigned to receive early Care Ecosystem training (intervention) and the remaining 15 assigned to received Care Ecosystem delayed training after the study period (control). The time period of interest for outcomes in intervention and control groups is the 6-month period between early and delayed training.

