5 RANDOMIZATION

The study team collaborated with iCMP leadership to identify 30 nurse care managers, prioritizing nurses who served the most disadvantaged practices. The selected nurses were randomly assigned using a randomization process in SAS to either early (intervention group) or delayed training (control group). Persons with dementia and their caregivers who meet inclusion / exclusion criteria were included in the study.

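### Nurses were randomised 15 v 15 and the protocol models them, but SAP 8.1 and 8.2 state no nurse effect, clustered variance or within-person link, and give no reason

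*SAP*

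**What the plan says.** SAP 3 and SAP 5 make the nurse care manager the unit of randomisation: 30 nurses, 15 to early and 15 to delayed training. Protocol 9.4 follows from this. Beside linear models it lists "negative binomial, or logistic regression, with random effects for nurses, to account for multiple patients nested within the same nurse", with training assignment as the main predictor.

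The outcome then changes between the documents. Protocol 9.3 has "The primary outcome for the is pilot is emergency room visits within 6 months". SAP 2.2 has "The primary outcome is the change in ED visits per member per month from the 12 months prior the adapted Care Ecosystem training"; the later window is the 6 months after it.

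Under SAP 8.1 the arms are "compared using a differences-in-differences model with a negative binomial distribution (to account for utilization count data) and log link". That section also gives a weight ("Models included a weight for the number of member months in the pre and post periods"), the excluded training month, the covariates and a sensitivity analysis that removes deaths. SAP 8.2 gives a linear difference-in-differences model with identity link and its covariates. SAP 7.2 adds the software ("SAS Enterprise Guide 7.1 is used for analyses") and the rule for choosing covariates.

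None of these sections mentions nurses as a model term, a robust or clustered variance, or how a person's pre and post records are tied together. None explains the departure from Protocol 9.4.

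**The concern.** Persons under the same nurse share that nurse's response to training, so the evidence for a training effect comes from 30 nurses and not from 231 independent persons. The protocol recognised this; the SAP is silent. The nurse term may have been dropped, or fitted and not written down. The text does not say which.

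Two omissions are possible, and they act in opposite directions. Ignoring differences between nurses in change makes standard errors too small. Treating a person's two rows as independent makes them too large.

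Reading Protocol 9.4 into the SAP does not settle the matter, because the SAP moved to a pre/post contrast. A constant nurse intercept largely cancels from that contrast. What matters is how much nurses differ in change.

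At stake is the stated precision of the ED rate ratio, which is the SAP's primary outcome analysis. Protocol 9.2 wants the pilot to support effect-size calculation for a full-scale study, so the width of that interval will be used.

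**Working it through.** **Inputs from the documents.** 15 v 15 nurses (SAP 3). ED cohort 126 v 105 persons (SAP 7.1.1). NPI-Q cohort 35 v 28 (SAP 7.1.2). The only design figure reproduces: 30 × 10 = 300 persons, 15 × 10 = 150 per arm. The documents give no ICC, design effect or power.

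**Assumed.** ICC of change 0.01 to 0.10; coefficient of variation (CV) of panel size 0 to 0.5; pre/post correlation ρ as shown; all 30 nurses contribute; two-sided 0.05.

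**1. Nurse clustering alone, ED visits.** Persons per nurse: 126/15 = 8.4 and 105/15 = 7.0; overall m = 231/30 = 7.7.

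Design effect DE = 1 + ((1 + CV²)m − 1) × ICC. True/reported SE = √DE. Coverage of a nominal 95% interval = 1 − 2(1 − Φ(1.96/√DE)).

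| ICC | DE, CV 0 | SE ratio | Coverage | DE, CV 0.5 | SE ratio | Coverage |
|---|---|---|---|---|---|---|
| 0.01 | 1.067 | 1.033 | 94.2% | 1.086 | 1.042 | 94.0% |
| 0.05 | 1.335 | 1.155 | 91.0% | 1.431 | 1.196 | 89.9% |
| 0.10 | 1.670 | 1.292 | 87.1% | 1.863 | 1.365 | 84.9% |

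With arm-specific panel sizes, (DE₁/126 + DE₂/105)/(1/126 + 1/105) runs from 1.066 to 1.855, which is practically the same. Simulated change scores (6000 runs, ICC 0.01 to 0.10) gave coverage of 94.1% down to 85.2% with nurses ignored, and 94.6% to 95.2% with a leave-one-nurse-out jackknife and t on 28 df.

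**2. Adding unlinked pre and post rows.** True/reported SE = √((1 − ρ) × DE), taking equal variance in both rows. At DE 1.8625:

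- ρ = 0.2: √(0.8 × 1.8625) = 1.22
- ρ = 0.5: √(0.5 × 1.8625) = 0.97
- ρ = 0.7: √(0.3 × 1.8625) = 0.75

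The two errors balance at ρ = 1 − 1/DE, which is 0.06 for the smallest DE and 0.46 for the largest.

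**3. A constant nurse intercept.** True/reported SE in simulated two-row linear data (3000 runs, equal panels):

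| ICC of change | ρ = 0, no nurse term | ρ = 0, intercept | ρ = 0.6, no nurse term | ρ = 0.6, intercept |
|---|---|---|---|---|
| 0 | 0.96 | 0.99 | 0.63 | 0.66 |
| 0.05 | 1.11 | 1.15 | 0.73 | 0.76 |
| 0.10 | 1.26 | 1.32 | 0.82 | 0.86 |

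The intercept does not repair the standard error.

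**4. Negative binomial check.** Two rows per person, 126 v 105 persons, 15 v 15 nurses, an assumed 0.08 visits per member per month, person SD 0 to 1.0 and nurse-by-period SD 0 to 0.4 on the log scale, 600 runs per setting, without the SAP's weights and covariates. Type I error at nominal 0.05 (simulation error about ±0.02):

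- neither link: 0.003 to 0.125
- clustering on person only: 0.053 to 0.173
- clustering on nurse, t on 28 df: 0.043 to 0.072

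**5. NPI-Q distress.** m = 63/30 = 2.1. DE runs from 1 + 1.1 × 0.01 = 1.011 to 1 + (1.25 × 2.1 − 1) × 0.10 = 1.1625. With a change score the reported SE is 1 − 1/√DE = 0.5% to 7% too small, and coverage is 94.9% to 93.1%. Poisson scatter at this mean gives CV 1/√2.1 = 0.69. At ICC 0.10 that raises DE to 1.21, makes the SE 9% too small and gives coverage of about 92.5%.

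**The case against.** This is a feasibility pilot. SAP 8.1 says there was no specific hypothesis about ED impact. The table of measures in Protocol 6 places feasibility of ED collection under the primary objective and the difference between cohorts under the secondary one. No outcome alpha or ED decision rule is given. SAP 8.2 judges NPI-Q against a 2-point estimate, which does not depend on a standard error. The SAP does not withdraw Protocol 9.4, so the two could be read together, and random effects for nurses need not mean only an intercept. Every ICC, CV and correlation is assumed. The formulas are linear, ignore the SAP's weights and covariates, and take equal variance for periods of 12 and 6 months; adjustment for baseline utilisation could lower ρ.

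Much of this stands, and it limits the consequence to precision, mainly for ED visits. The figures are illustrative and no single direction can be claimed. It does not remove the point. SAP 8.1 still makes a between-arm rate ratio its primary outcome analysis, and the negative binomial check shows that error rates can be well off in either direction without the two links. If Protocol 9.4 was meant to carry over, the SAP must say in what form, because an intercept alone would not serve the changed outcome.

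**Conclusion.** The concern holds and should be fixed. The SAP omits, without a reason, the clustering that the design requires and the protocol specified. It does not establish that the fitted models ignored nurses. If they did, the ED standard error is 3% to 36% too small in relation to the reported value when pairing was handled. If a person's rows were also unlinked, the error can be smaller or reversed (true/reported SE down to 0.75 at the largest design effect and ρ = 0.7). The within-person gap bears mainly on SAP 8.1, because a log-link count model implies two rows per person, whereas a linear change score in SAP 8.2 would link the surveys by construction. NPI-Q adds little weight at about two respondents per nurse. All sizes rest on the assumed ICC, CV and ρ.

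**What to change.** In SAP 8.1 and 8.2:

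1. State the data layout: two rows per person, or a change score.
2. State how nurse clustering and repeated records were handled. Standard errors clustered on nurse are adequate and also cover a person's two rows; use a small-sample correction and t with contributing nurses minus 2 degrees of freedom (28 if all 30 contribute). A mixed model with person and nurse-by-period effects is an alternative. A constant nurse intercept alone is not enough.
3. Report the contributing nurses per arm and the nurse-level variance of change, which a later nurse-randomised study will need.
4. If nurse effects were left out on purpose, say so and why, and label the intervals as not accounting for nurse randomisation.

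The cost is one SAP paragraph and a few lines of code, with no new data. Intervals may widen or narrow. The t quantile alone widens them by 4.5% (2.048/1.960 = 1.045), and the clustered variance rests on at most 30 nurses.

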The integrated care management program (iCMP) within Mass General Brigham is a nurse-led longitudinal care management program embedded in Primary Care practices across the Mass General Brigham network that provides care management support to the most medically complex and seriously ill patients. iCMP care managers assess each patient to clarify problems, identify barriers to accessing clinical care and community-based services, including the social determinants of health, and create a patient-centric care plan. The iCMP program serves all payor populations and has cared for over 38,000 patients since 2012. Approximately 14,000 patients are presently enrolled in iCMP, 64% of whom are Medicare beneficiaries. An independent evaluation of Medicare patients in iCMP, relying on 18 months of claims data post-iCMP assessment, found an average savings in total medical expense (TME) of \$101 per member per month¹⁰. iCMP teams care for many patients with dementia, but are not specifically trained in the care of persons

with dementia (PWD) and their caregivers. iCMP care managers have described lower levels of self-efficacy in the care of PWD. An analysis of cognitive disorders within the Mass General Brigham system identified a conservative estimate of dementia prevalence of 8.8% among iCMP Medicare patients based on ICD-10 diagnosis codes for dementia, as compared to a roughly 5.1% prevalence of dementia among all Medicare patients. Thus, the iCMP program provides an opportunity to train nurse care managers in an adapted CareEco model for dementia patients.

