6 SAMPLE SIZE

Preliminary estimates based on 2018 data suggested that on average FTE iCMP nurse care managers in our health system have 10 Medicare beneficiaries diagnosed with dementia on their panels. For this pragmatic quality improvement trial, we planned to engage 30 active iCMP nurse care managers (out of a total of approximately 65 nurse care managers) serving approximately 300 PWD and their caregivers (150 in each arm).

Among the 30 nurse care managers actually selected for the study, a total of 393 PWD met the inclusion criteria, 206 patients corresponding to the 15 intervention nurses and 187 patients corresponding to the 15 control nurses. The population was refined to exclude patients without a designated caregiver, deceased or moved to skilled nursing facility (for full list of exclusions see Figure 1 of cohort flowchart). This validated cohort included 143 PWD in the intervention group, and 113 PWD Controls.

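### The SAP's ED model states no variance for the paired pre/post records and no nurse term, so with the ordinary model-based variance its interval would usually be miscalibrated

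*SAP*

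**What the plan says.** SAP 2.2 defines the outcome as a rate: "The primary outcome is the change in ED visits per member per month", from the 12 months before training to the 6 months after. SAP 8.1 says the arms are "compared using a differences-in-differences model with a negative binomial distribution (to account for utilization count data) and log link". On exposure it adds: "Models included a weight for the number of member months in the pre and post periods". Its listed covariates are baseline utilization, race, ethnicity and age.

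Neither SAP 8.1 nor SAP 7.2-7.3 names an offset, the scaling of the weight, a variance estimator, a term for the two records per PWD, or a nurse term. SAP 7.2 names the software but no procedure.

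Nurses were the randomised unit. SAP 3 says: "15 integrated care management program (iCMP) nurse care managers were randomly assigned to receive early Care Ecosystem training", with 15 more assigned to delayed training. Protocol 9.4 plans regression "with random effects for nurses, to account for multiple patients nested within the same nurse". The SAP neither repeats this nor explains its absence.

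**The concern.** Three features of the data bear on the standard error: unequal exposure, two correlated records per PWD, and PWD nested within 30 randomised nurses. The SAP text addresses only the first, through a weight whose role is open. The response is open too: the outcome is a rate, while the family is justified by counts.

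A model-based variance treats the records as independent. It also takes the scale of the weight at face value, so multiplying all weights by a constant changes the standard error. The same data could therefore give an interval that is too narrow or much too wide, and a reader of SAP 8.1 cannot tell which.

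Protocol 9.2 intends the pilot to inform effect sizes for a full-scale study. A misstated standard error would give those planners false precision or false uncertainty about the ED effect.

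**Working it through.** **No figure to reproduce.** The documents give no ED rate, dispersion, intracluster correlation, standard error or interval for this outcome.

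**Inputs from the documents.** 126 intervention and 105 control PWD, with at least 1 member month in each period (SAP 7.1.1); 15 + 15 nurses (SAP 3); 12 months before and 6 months after training (SAP 2.2).

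**Assumptions.** ED rate 0.05-0.50 PMPM; frailty variance (k) 1-3; pre/post frailty correlation 0.5-1; nurse and nurse-by-period SD 0 or 0.2; 80% of PWD with full exposure; no covariates. Rates up to 0.50 are included because the programme "provides care management support to the most medically complex and seriously ill patients".

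**Step 1: why the weight's scale matters for a PMPM response.** The true variance of a PMPM over m months is μ/m + kμ². A negative binomial fitted to the rate implies at least μ.
- At μ = 0.10, k = 1, the 6-month variance is 0.10/6 + 0.01 = 0.027 and the 12-month variance is 0.10/12 + 0.01 = 0.018. Both are below 0.10, so the fitted dispersion goes to 0 and the weight's scale largely sets the standard error.
- At μ = 0.50, k = 3, the 6-month variance is 0.50/6 + 0.75 = 0.83. This is above 0.50, so the dispersion can stay positive.

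In simulation with raw weights, the fitted dispersion was 0 in 100% of trials at 0.05-0.20 PMPM and in 0-1% at 0.50 PMPM with variance 3.

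**Step 2: coverage of the model-based 95% interval** (25 scenarios × 600 trials; Monte Carlo error about 0.9 points):

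| Reading of SAP 8.1 | Coverage |
|---|---|
| PMPM, raw weights, 0.05-0.20 PMPM, correlation 0.5-0.8 | 78.8-93.7% |
| PMPM, raw weights, 0.30-0.50 PMPM, correlation below 1 | 61.3-89.0% |
| PMPM, raw weights, correlation 1 | 94.5-96.2% |
| PMPM, normalised or dispersion weights | 98.7-100% (SE 1.2-3.0 × true SD) |
| Counts, raw weights, with or without offset | 54-82% in 24 of 25 scenarios |
| Counts, offset, no weight | 97.0-100% (SE 1.06-3.4 × true SD) |

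The exception for raw-weighted counts is 0.50 PMPM, variance 3, correlation 1 (97.3-97.8%).

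A second simulation (six scenarios, 0.10-0.25 PMPM, nurse-by-period SD up to 0.3) gave 78-93% for PMPM with raw weights and 48-65% for raw-weighted counts. PMPM with normalised or dispersion weights gave 99.8-100%. Counts with an offset gave SE/SD of 0.97-1.25 unweighted and 1.01-1.31 with normalised weights. A third (three scenarios × 200 trials) gave 74-94% for PMPM with raw weights, 100% for PMPM with normalised weights and 46-57% for raw-weighted counts.

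**Step 3: one example.** Rate 0.10 PMPM, variance 1, correlation 0.5, rate ratio 1. The true SD of the log rate ratio is 0.245-0.257 across models. The interval is exp(±1.96 × SE), or exp(±2.05 × SE) for t on 28 df.

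| Variance used | Median SE | SE/SD | Interval |
|---|---|---|---|
| True SD (0.245) | – | 1 | 0.62-1.62 |
| PMPM, raw weights | 0.221 | 0.86-0.90 | 0.65-1.54 |
| PMPM, dispersion weights | 0.596 | 2.32-2.43 | 0.31-3.22 |
| PMPM, normalised weights | 0.633 | 2.46-2.58 | 0.29-3.46 |
| Counts + offset, raw weights | 0.109 | 0.42-0.44 | 0.81-1.24 |
| Counts + offset, nurse-clustered, t28 | 0.263 | 1.02-1.07 | 0.58-1.71 |

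**Step 4: clustering on nurse.** Both records of a PWD lie within one nurse's cluster, so this also covers the pairing. With the Mancl-DeRouen correction and t on 30 − 2 = 28 df, coverage was 93.7-97.5% in all four models tested, and 95.5-97.5% in the third simulation. An uncorrected nurse-clustered sandwich with t28 gave 92-96% in the second. Random effects for nurse and PWD gave 94.0-98.0% (4 scenarios × 150 trials; Monte Carlo error about 1.8 points).

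**Step 5: the rate ratio.** With a true value of 0.80, the weighted PMPM and offset models gave means of 0.802 vs 0.802 and 0.794 vs 0.792.

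For raw-weighted counts without an offset, effective exposure is E[m²]/E[m]. Assume a share p of PWD has post-period exposure spread evenly over 1-5 months and the rest have 6:
- p = 0.10: 33.5/5.7 = 5.88
- p = 0.25: 29.75/5.25 = 5.67
- p = 0.40: 26.0/4.8 = 5.42

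Truncation of 25% vs 10% multiplies the rate ratio by 5.67/5.88 = 0.96, and 40% vs 10% by 5.42/5.88 = 0.92. In simulation the 25% vs 10% shift was about 4-6%.

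**The case against.** The strongest reply is that the SAP is silent rather than wrong. No variance estimator is named, and if a nurse-clustered robust variance was run, the interval problem disappears. That stands: a reader might infer that the trial's ED interval is wrong, and the documents do not show this. They show a model that, with its ordinary variance, would usually be miscalibrated, and no statement that another variance was used.

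Second, the weight may already do the offset's work. With a PMPM response y = n/m, raw weights and fitted dispersion 0, the weighted log-likelihood m(y log μ − μ) equals n log μ − mμ, which is a Poisson count model with offset log(m). This stands too. The weight is not an error in itself, and an offset alone does not calibrate the interval.

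Third, a reader might infer that the nurse effect of protocol 9.4 is itself inadequate. The documents do not support that. Protocol 9.3 takes ED visits within 6 months as the outcome, and 9.4 describes a regression on arm with baseline covariates, not stacked pre/post records. All that can be said is that in the SAP's two-record model a nurse intercept alone does not handle the pairing.

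Fourth, the coverage figures rest on assumed rates, dispersion and correlation. True: how often the interval is off describes the assumed range, not this trial's data. Nor is every alternative reading far too wide. Counts with an offset and no weight, or a normalised weight, are near nominal to moderately too wide in most scenarios.

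Finally, the objective is feasibility and SAP 8.1 states no ED hypothesis. That limits the consequence but does not remove it.

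**Conclusion.** The point holds as a should-fix, with medium confidence. SAP 8.1 states neither a variance that respects the paired records nor a nurse term, although nurses were randomised and protocol 9.4 specifies nurse effects.

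If the model-based variance is used, the interval is miscalibrated over most of the assumed range, in a direction the text leaves open. It is usually too narrow with raw weights: about 61-94% coverage for PMPM at correlation below 1, and 46-82% for counts in nearly all scenarios. It is much too wide for PMPM with normalised or dispersion weights.

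The rate ratio is essentially unaffected for a PMPM response or counts with an offset. A reader might extend that to every reading, but counts without an offset can shift by about 4-8% if member months differ by arm.

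No efficacy decision depends on this interval. What is at stake is the stated precision of a pilot estimate.

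**What to change.** First state in SAP 8.1 what was run: the response (count or PMPM), any offset, how the weight entered and was scaled, and the variance estimator. If a nurse-clustered or equivalent variance was used, correcting the text is enough.

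Otherwise keep the point-estimate model (weighted PMPM, or in effect the same, counts with offset log(member months) and no weight) with its arm, period, arm-by-period and covariate terms, and add wording such as:

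*The variance is clustered on nurse care manager, which also covers the two records per PWD, with a small-sample correction (for example Mancl-DeRouen, with t on 28 degrees of freedom).*

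Random effects for both nurse and PWD are an acceptable alternative. Explain the departure from protocol 9.4.

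Report the refit beside the model as specified and label it post hoc, because the SAP already gives cohort counts ("Among the 30 nurse care managers actually selected for the study, a total of 393 PWD met the inclusion criteria") and observed imbalances ("race, ethnicity, and age were identified as different between intervention and control in the Utilization Outcome Cohort").

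The cost is one refit of existing data and a revised paragraph, with no new data collection. The interval may become wider or narrower.
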